4.2.2 Blind state/Breaking blindness

This study will not be conducted in a blinded manner.

5. Subject population

The subjects of this study are children and adolescents aged 6-18 years old.

5.1 Diagnostic criteria: Foot pain diagnosis is based on facial VAS score, foot posture evaluation is based on foot posture index, foot 3D scanning and weight-bearing position foot X-ray, plantar soft tissue development evaluation is based on plantar ultrasound, bone growth and development evaluation is based on left wrist bone age, gene analysis uses saliva samples, traditional Chinese medicine syndrome analysis uses the Four Diagnostic and Traditional Chinese Medicine Tongue Image Intelligent Analysis System, gait and training motion dynamics analysis uses optical motion capture combined with virtual simulation technology, etc.

5.2 Inclusion criteria:

- 1) Agree to participate in the study, and the legal representative voluntarily signs the informed consent form
- 2) Children and adolescents aged 6-18 with typical development, regardless of gender

5.3 Exclusion criteria

- 1) Besides flat feet, there are other congenital deformities of the lower limbs or spine that affect foot posture
- 2) History of muscle, nerve, and bone diseases that affect foot posture, except for flat feet
- 3) According to the researcher's judgment, it is not suitable to participate in this study

5.4 Exit criteria

All enrolled subjects have the right to withdraw from this study at any time.

Participants who withdraw from the study for any reason must record their reasons, including the following:

- 1) The subject withdraws the informed consent form;
- 2) Subject lost to follow-up;
- 3) The legal representative of the subject refuses to continue the follow-up visit;
- 4) The researchers believe that for other reasons, the subjects are not suitable to continue participating in this study;

Participants who withdraw from the study midway are considered dropout samples. When the subject falls off, efforts should be made to obtain as much as possible contact, complete the evaluation project, and fill out the research summary page.

5.5 Termination criteria

Termination criteria (terminated if any of the following criteria are met):

- 1) Serious safety issues occurred during the experiment;
- 2) Significant errors were found in the clinical trial protocol during the trial;
- 3) The ethics committee requests the termination of the experiment;

6. Research instruments

- 1) Height and weight measurement: using ultrasonic ranging and pressure sensors
- 2) Body fat analysis: using bioelectrical impedance method to analyze the muscle fat ratio of the human body
- 3) Foot 3D scanner: using structured light, Class 2M, harmless to the human body and eyes
- 4) S-TAG all-weather wearable sensor: using inertial measurement unit (IMU), including gyroscope and accelerometer
- 5) VICON optical motion capture system: (produced by Oxford Metrics Limited, UK), sampling frequency 100Hz; Mainly including hardware and software facilities, the hardware part includes 8 cameras, MX components, PC host, information conversion box, calibration T-frame, reflective marker ball, and other accessories; The software part mainly consists of VICON Nexus software.
- 6) Vertical Rhythm Platform (WBV): Adjustable frequency, 3mm vertical synchronous vibration
- 7) Traditional Chinese Medicine Tongue Analysis System: An Image Recognition and Analysis System Based on Artificial Intelligence
- 8) Bone age DR system: using lead plates with micro radiation protection for movable wrist measurement
- 9) Bone density ultrasound: measurement with a fully dry (no temperature control device required) oil bag probe, bidirectional ultrasound transmission and reception. No radiation, suitable for testing various populations (children, pregnant women, adults, and elderly). It is recommended to test within the age range of 3-100 years old (actual testing can be conducted within 0-100 years old).

7. Research methods and steps

As this is an experimental study, researchers will select the children to be included according to the research protocol. Researchers will inquire about the medical history of the child's guardian and conduct a physical examination of the child to determine their eligibility based on inclusion and exclusion

criteria. The guardian of the child must sign the latest IRB/IEC approved informed consent form (ICF) before conducting data collection. The frequency and duration of visits shall be determined by the doctor in accordance with the usual practice of the research plan.

7.1 Screening period:

All subjects are required to complete screening period related examinations before enrollment and be screened according to inclusion and exclusion criteria.

- 1) Sign informed consent form
- 2) Record demographic data: date of birth, gender, initials;
- 3) Anthropometry: including height, weight, and length of both lower limbs
 - ① Measurement of length of both lower limbs

Measurement position: supine position, lower limbs extended, pelvis in neutral position, hip joint in neutral position.

Measurement method: Use a soft tape to measure the shortest distance from the anterior superior iliac spine to the medial malleolus, measure the left and right legs separately, and record the results in the test registration form.

- ② height

Measurement method: The subject stands barefoot in a "upright" position, with their heels, sacrum, and shoulder blades tightly against the wall. The measurer can stand on either side of the person being measured, adjust their head to the lowest point between the upper edge of the tragus and the lower edge of the eye socket, and start the height measuring device to measure their height.

Measurement requirements: The height should be measured barefoot each time, using the same measuring instrument at the same time (more accurately in the morning), with the same person measuring as much as possible, and the body posture should be consistent before and after. Each measurement of height requires two consecutive measurements with a 30 second interval. The results of the two measurements should be roughly the same, and the error in height should not exceed 0.5 centimeters.

- ③ weight

Testing method: Wear lightweight clothing, stand barefoot, naturally on an electronic weight scale, measure weight twice in a row with a 30 second interval. The results of the two measurements should be roughly the same, and the error in weight should not exceed 0.5KG.

4) Facial VAS score for foot pain

The subjects represent the degree of foot pain by selecting the corresponding pattern on the scale.

[figure not shown]

Figure 1 Facial VAS score for children: representing foot pain by selecting the corresponding pattern on the scale degree

7.2 Phase One

We plan to recruit 1000 participants aged 6-18 to record their basic health status and static foot posture at baseline. Subsequently, sensors were used to collect gait data for more than 8 hours per day for the next 4 weeks, and all enrolled children wore wearable sensors in their daily lives. The obtained data is uploaded to the cloud server through a mobile application, and remote monitoring and daily event recording are achieved by uploading the data through the APP. When subjects experience foot pain events, they should promptly report to the researchers through the APP. After determining foot pain based on VAS scores, the subjects with foot pain will be enrolled in the observation group, exercise intervention group, and WBV intervention group according to their wishes. Children in the observation group should rest according to medical advice and not participate in sports activities. Children in the intervention group received WBV vertical rhythm or exercise training programs under the guidance of researchers' follow-up. The follow-up time is once a week, and the training lasts for a total of 4 weeks. Using a self-developed app for researchers to remotely monitor and guide children's training movements, and track training progress.

The device uses Huawei S-TAG foot rings, matched with HarmonyOS 2+/Android 6.0+/iOS 9.0+systems; IP68 (GB/T 4208-2017), waterproof rating of 50 meters; Bluetooth: BT 5.0 transmits data; Running Scene

Battery life: Run for 1 hour per day, run 5 days a week, leave it still when not in use, and have a battery life of 30 days.

(1) WBV Vertical Rhythm Training Standard Process: Children enrolled in the study will be trained at home using vertical rhythm equipment under the guidance of researchers and parental supervision. WBV training lasts for 4 weeks, five days a week, with 15 minutes of training per day. Each movement lasts for 30 seconds, and there is a 30 second break between groups.

(2) Standard process for traditional Chinese medicine exercise training: Children enrolled in the group will undergo exercise training under the supervision of their parents, following the teaching of a self-developed APP. The Yi Jin Jing training will last for 4 weeks, five days a week, with 15 minutes of training per day. There will be a total of 12 exercises, each lasting 1 minute, with a 15 second break between groups.

Figure 2 S-TAG Wearable Sensor

7.3 Phase 2

120 children aged 8-10 years were selected for an observational study on foot development and growth development, without grouping, and no intervention procedures were performed in this stage of the study. The following is the collected data:

Foot three-dimensional morphology: Using harmless and radiation free structured light three-dimensional scanning to obtain foot three-dimensional morphology parameters. The subject stood barefoot on a 3D foot scanner and tested their left and right feet separately.

Figure 3 Schematic diagram of 3D scanning of foot morphology

- 1) Static foot posture: FPI-6 foot posture index, weight-bearing position foot X-ray
- 2) Bone age analysis: using lead plates with micro radiation to protect the movable wrist and measure bone age
- 3) Bone density analysis: Measurement of bone density in the calcaneus using musculoskeletal ultrasound
- 4) Genomic grouping: Collecting saliva from children for whole genome analysis
- 5) Body fat analysis: Evaluating body fat ratio using bioelectrical impedance method
- 6) Traditional Chinese Medicine Constitution Evaluation: Using the Traditional Chinese Medicine Body Mass Scale combined with tongue image analysis, "Classification and Identification of Traditional Chinese Medicine Constitution in Children in Guangdong Province" (T/GDACM 0112-2022)

7.4 Phase Three

Select 30 children aged 8-10 for laboratory testing. This stage is an observational study without grouping.

Passive optical motion capture system, using a floodlight sphere attached to various parts of the human body as marker points, driven by motion capture the camera for spatial positioning and record the motion trajectory. The ground reaction force of gait is obtained through the plantar pressure plate. The surface muscle activation force is collected through a 16 channel Delsys surface electromyography testing system: Noraxon bipolar disposable surface electromyography electrodes are used, with a distance of 20mm between the electrodes. Used to collect the maximum voluntary contraction (MVC) of 4 hip and knee muscles and 11 ankle muscles of the subjects, as well as the muscle strength change curves and maximum force values during training, with a frequency set at 1000 Hz for model validation.

This technology is mature, with high accuracy, high sampling rate, and wireless, non luminous, non heating, non radiative, and non-invasive detection. Motion capture systems have provided comprehensive solutions for nearly a thousand users worldwide, widely used in fields such as motion analysis and animation production.

Figure 4 Optical motion capture device

The collected actions are as follows:

- 1) Gait analysis: Children walk 10 meters on the plantar pressure plate at their own pace and collect dynamic parameters during the gait process.
- 2) Analysis of martial arts movements: Children stand on a plantar pressure plate and collect dynamic parameters of the training movements of the Yi Jin Jing.

[figure not shown]

Figure 5 Schematic diagram of optical motion capture in traditional Chinese medicine exercises

- 3) Analysis of WBV Vertical Rhythm Training Actions: The subjects stand on a vertical rhythm platform, adopt different heel lifting or squatting postures, maintain static posture for 30 seconds, and collect dynamic parameters during the period.

[figure not shown]

Figure 6 Schematic diagram of WBV rhythm training

Finite element analysis: Reconstruct muscle bone models from Dicom format files of children's MRI scans, and use the muscle activation force obtained from motion capture parameters in virtual simulation as boundary conditions for finite element analysis of structural stress in areas such as the feet and waist.

[figure not shown]

Figure 7 Schematic diagram of finite element analysis

8. evaluating indicator

The first stage is a prospective intervention study, in which children who experience foot pain events are trained and intervened until the end of a 4-week intervention period, and the evaluation of efficacy indicators is considered the endpoint of the rehabilitation study. The second and third stages are observational studies, where participants' participation in laboratory testing on the same day is considered the endpoint.

8.1 Main efficacy indicators

Dynamic Foot Posture: Gait Push Off Period Foot Outward Angle

Capture the angle of foot valgus during gait push off period through wearable devices, and compare the difference between the values after intervention and before intervention.

[figure not shown]

Figure 8 Schematic diagram of wearable sensor dynamic foot axis

The red dashed line represents the longitudinal axis of the foot, and through wearable sensors, the angle of this axis relative to the reference axis during the stance phase of gait can be calculated.

8.2 Secondary efficacy indicators

Static foot posture is evaluated using the Foot Posture Index FPI-6.

The FPI score should be an integer between -12 and 12, with $12 \geq FPI \geq 8$ indicating severe pronation posture, $8 > FPI \geq 4$ indicating mild pronation posture, $-12 \geq FPI \geq -8$ indicating severe supination posture, $-8 > FPI \geq -4$ indicating mild supination posture, and $4 > FPI > -4$ indicating neutral posture.

9. Safety monitoring, reporting, and medical treatment

9.1 Definition of Adverse Events (AE)

Adverse events refer to any adverse medical events that occur after a patient or subject receives a drug, which may not necessarily be causally related to the treatment. Therefore, adverse events can be any adverse signs (including abnormal laboratory results), symptoms, or diseases that are temporally related to the use of the study drug, regardless of whether a causal relationship with the study drug is considered. Adverse events include Serious Adverse Events (SAEs) and Non Serious Adverse Events.

9.2 SAE Definition

SAE refers to medical events that occur during clinical trials that require hospitalization or prolonged hospitalization, disability, affect work ability, endanger life or death, or cause congenital malformations. Including the following medical events:

- 1) Events leading to death;
- 2) Life threatening events (defined as the risk of immediate death for the subject at the time of the event);
- 3) Events that require hospitalization or prolonged hospitalization;
- 4) Events that can lead to permanent or severe disability/functional impairment/affect work ability;
- 5) Congenital abnormalities or birth defects;

Other important medical events (defined as events that endanger the subjects or require intervention to prevent any of the above situations from occurring).

9.3 Adverse event recording, collection, reporting, and handling

9.3.1 Definition of Adverse Events (AE):

AE is any adverse medical event that occurs in clinical research subjects and is time related to the use of research treatment interventions, regardless of whether it is considered related to the

research treatment interventions. Therefore, AE can be any adverse and unexpected signs (including abnormal laboratory results), symptoms, or signs that are time-dependent with the use of research treatment interventions, condition or disease (new or aggravated).

Definition of Serious Adverse Event (SAE):

SAE refers to medical events that occur during clinical research that require hospitalization or prolonged hospitalization, disability, affect work ability, endanger life or death, or cause congenital malformations. Including the following medical events:

- 1) events leading to death;
- 2) Life threatening events (defined as the risk of immediate death for the subject at the time of the event);
- 3) Events that require hospitalization or prolonged hospitalization;
- 4) Events that can lead to permanent or severe disability/functional impairment/affect work ability;
- 5) Congenital abnormalities or birth defects;

Other important medical events (defined as events that endanger the subjects or require intervention to prevent any of the above situations from occurring).

Definition of Suspected and Unexpected Serious Adverse Reaction (SUSAR):

Suspected and unexpected serious adverse reactions that exceed the nature and severity of the clinical presentation beyond existing information such as the investigational drug investigator's manual, marketed drug instructions, or product characteristic summaries

9.3.2 Collection, reporting, and processing of AE

All adverse events related to the operating procedures specified in the trial protocol that occur between the signing of the informed consent form and the administration of the investigational drug must be recorded in the APP database.

The record of AE should include: description of AE and all related symptoms, occurrence time, severity, duration, relevance to the investigational drug, measures taken, and final results and outcomes. The recording of AE must use medical terminology, and if the symptoms and signs of the subjects can be summarized by a common cause, the diagnostic results should be recorded as much as possible. Except for indicators related to disease progression, all clinical events and clinically significant laboratory adverse reactions can be treated according to the Common Adverse Reaction Event Evaluation Criteria (CTCAE) version 5.0. Adverse reactions caused by treatment will be recorded by researchers.

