Inclusion Criteria	Agree to participate in the study, and the legal representative voluntarily signs the informed consent form Children and adolescents aged 6-18 with typical development, regardless of gender

Exclusion criteria	Except for flat feet, there are other congenital deformities of the lower limbs or spine that affect foot posture. In addition to flat feet, there are other muscle, nerve, and bone diseases that affect foot posture. The researchers have determined that they are not suitable to participate in this study
Effectiveness analysis	Main efficacy indicators: Motional foot posture improvement (push off phase foot flip angle) Secondary efficacy indicators: Static foot posture improvement (foot posture index FPI-6)
Security analysis	The detection equipment and methods used in this study mainly include harmless optical motion capture, structured light 3D scanning, wearable sensors, and bioelectrical resistance body composition analysis; X-ray, bone age, ultrasound and other imaging tests are all operated by professional technicians, and the collection environment and methods meet safety requirements; The intervention method is non pharmacological therapy, which is harmless to the human body; The data acquisition and analysis process strictly follows privacy protection regulations, and there is no security risks.
statistical analysis	Analysis set: Use the full analysis set for statistical analysis. Full analysis set (FAS): Includes all enrolled subjects who have received at least one non pharmacological intervention and have measurable baseline foot injury. Sample size determination: According to epidemiological surveys, the incidence of foot pain events in children is about 12%, and it is determined based on similar studies. Statistical analysis: SPSS 25.0 statistical analysis software will be used for statistical analysis
follow-up	Feedback on foot pain events; Execution of martial arts training and vertical rhythm training; The efficacy and adverse reactions of martial arts training and vertical rhythm training.
Statistical methods	The method used is independent sample t-test to analyze gait parameters of normal and poor foot postures, and repeated measures ANOVA to analyze gait and foot posture parameters before and after intervention.

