9.3.3 Collection and reporting of SAE

All SAEs that occur within 4 weeks after the subjects sign the informed consent form and complete the study, regardless of their cause or drug relevance, must be reported using the SAE

report form. If a serious adverse event (SAE) occurs, the researcher should immediately take appropriate treatment measures for the subjects to ensure their safety. At the same time, the researcher should report to the drug registration applicant, the National Medical Products Administration, the Provincial Food and Drug Administration, the ethics committee of the corresponding clinical trial center, and the Medical Department of the Health Commission and Medical Administration Bureau within 24 hours, and promptly report to the ethics committee of the leading unit. The first report should include the following information as much as possible: source of the report, name of the investigational drug, name of serious adverse event, time of occurrence, severity, duration, relevance to the investigational drug, measures taken, and outcome.

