9.3.4 Criteria for determining the severity of AE

Researchers will evaluate the severity based on the five level judgment criteria developed by NCI CTCAE 5.0:

- Level 1, mild; Asymptomatic or with mild signs; For clinical or diagnostic observation only, no medical intervention is required;
- Level 2, moderate; Age appropriate daily life functions are restricted (such as cooking, shopping, making phone calls, etc.);
- Level 3, severe or medically significant but not immediately life-threatening; Causing hospitalization or prolonging hospitalization time; a disability; Restricted daily self-care activities (daily self-care activities refer to bathing, dressing, undressing, eating, toileting, taking medication, etc., but not bedridden);
- Level 4, life-threatening, requiring emergency treatment;
- Level 5, AE related deaths;

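### Section 9.3.2 ties mandatory adverse event recording to drug administration in a drug-free trial, so no sentence requires non-serious events of any cause to be recorded during the 4-week training or observation

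*Protocol*

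**What the plan says.** The protocol summary (Security analysis) states: "The intervention method is non pharmacological therapy". Its follow-up row lists, among other items: "The efficacy and adverse reactions of martial arts training and vertical rhythm training".

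Section 9.3.2 contains two statements on which adverse events are recorded:

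- The first is mandatory. It covers events related to the protocol's operating procedures "that occur between the signing of the informed consent form and the administration of the investigational drug must be recorded in the APP database".
- The last sentence of the section reads: "Adverse reactions caused by treatment will be recorded by researchers". It gives no time window and no place of recording.

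The two definitions of an adverse event are broad as to cause. Section 9.1 includes events "regardless of whether a causal relationship with the study drug is considered", but only once the subject has received a drug. Section 9.3.1 covers an event that "is time related to the use of research treatment interventions, regardless of whether it is considered related to the" intervention. The two also differ in other respects: 9.3.1 asks that signs be unexpected and mentions new or aggravated conditions.

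Section 9.3.3 sets the rule for serious events: "All SAEs that occur within 4 weeks after the subjects sign the informed consent form and complete the study, regardless of their cause" or relation to a drug.

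**The concern.** Section 9 carries drug-trial wording into a trial without a drug. In most places that is cosmetic. In 9.3.2 it is not, because the drug marks the end of the recording window, and the sentence is also restricted by cause.

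What is at stake is the safety record of the two trainings in children. The summary names their adverse reactions as follow-up content. The study is unblinded (4.2.2) and children join groups by preference (4.2.1). If a non-serious event is written down only after someone has judged that the training caused it, an unexpected effect can go unrecorded because nobody recognised it as one. The observation group could show how often such events occur without training, but no clear rule collects them there beyond procedure-related events.

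**Working it through.** No arithmetic applies: the protocol gives no adverse event rate, and the point rests on no sample size or power figure. The check is to ask, for each kind of event during the 4-week period, which sentence requires it to be recorded.

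**Step 1: when does the mandatory window close?** Two readings are possible.

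- *Literal.* No drug is ever administered, so the window never closes. The sentence still covers only procedure-related events. Since 7.2 sets out both trainings as standard processes, events related to training would fall under it.
- *By analogy.* Drug administration stands for the start of the intervention. The window then closes before the 4 weeks of training or observation begin.

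**Step 2: coverage during the 4 weeks.**

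| Event | Literal reading | Window ends at start of intervention |
|---|---|---|
| Serious, any cause | 9.3.3 | 9.3.3 |
| Non-serious, judged caused by training | 9.3.2, first and last sentences | 9.3.2, last sentence |
| Non-serious, procedure-related, observation group | 9.3.2, first sentence | no clear rule |
| Non-serious, unrelated or of unclear cause, trained child | none | none |
| Non-serious, unrelated or of unclear cause, observation child | none | none |

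The last two rows are empty on either reading.

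**Step 3: does another section fill them?**

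- 9.1 and 9.3.1 are definitions and set no duty to record. Read literally, 9.1 applies to no child, since none receives a drug. 9.3.1 ties events to use of the research interventions, and observation children rest instead of training (7.2).
- The CTCAE sentence in 9.3.2 is permissive and concerns handling, not which events are to be recorded.
- 9.3.4 grades severity. Its lowest level includes the descriptor "For clinical or diagnostic observation only, no medical intervention is required", but grading presupposes a record.
- 7.2 mentions daily event recording through the app, but foot pain is the only event that it tells subjects to report. The weekly follow-up there comes directly after the intervention groups, so it is unclear whether it applies to observation.
- 14.5.1 refers to the requirements for serious events only.

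None of these states the missing rule.

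**The case against.** The strongest reply is that section 9.3, read as a whole, already points to recording all adverse events as defined. It opens with a definition that disregards cause, its list of record contents includes relatedness, and it grades events that need no intervention. A relatedness field has little purpose if only related events are entered. This is a fair account of the likely intention. It does not supply the instruction: the two sentences that say which events are recorded are both narrower, so the section disagrees with itself.

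Four stronger readings are tempting, and the protocol does not support them.

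- *That nothing need be recorded once training starts.* The last sentence of 9.3.2 is a commitment to record reactions caused by treatment, and serious events have their own rule.
- *That relatedness can never be judged in the observation group.* Those children follow a protocol instruction to rest (7.2) under researchers' guidance (3.2), so relation to procedures can be assessed. What is missing is a rule for everything else.
- *That serious events late in follow-up escape reporting.* Section 9.3.3 could be read as 4 weeks from consent, but its words on completing the study would then have no function. Consent to 4 weeks after completion uses every word and is the more natural reading. The sentence deserves clearer wording and no more.
- *That the trial's results are biased.* The efficacy endpoints do not depend on adverse event recording, and 13.3 plans no comparison of adverse events between groups.

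**Conclusion.** The point holds in a limited form. The mandatory recording sentence in 9.3.2 is restricted by cause and ends at an event that cannot occur in this trial. No other sentence requires non-serious events to be recorded regardless of cause during the 4-week training or observation.

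The practical gap is non-serious events judged unrelated, or of unclear cause, in trained children, and non-serious events in observation children beyond those related to procedures. It concerns the children with foot pain, planned as at least 34 in each of three groups. Those counts describe who is exposed to the gap and say nothing about how many events would be lost.

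The conclusion assumes that staff apply the text as written. If they already record every event in the app, the defect is one of wording only. It is a minor to moderate point that should be corrected, because the correction is simple and the subjects are children.

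**What to change.** Reconcile 9.1 and 9.3.1 to 9.3.3.

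1. Rewrite the first sentence of 9.3.2: for children with foot pain in all three groups, including observation, all adverse events regardless of cause are recorded in the app from consent to the end of the 4-week assessment. Merely exchanging the drug wording for the study intervention would not do, because the window would then close when the intervention starts.
2. In 9.1 and 9.3.1, define adverse events by study period or study participation. A definition that depends on receiving an intervention would still leave out observation children.
3. In the list of record contents, ask for relatedness to the study intervention or procedures instead of to a drug.
4. As a minor clarification, word the window in 9.3.3 plainly as consent to 4 weeks after completion, if that is what is meant.

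The cost is a change of wording, somewhat more app entries, and the same adverse event enquiry in observation as in the trained groups. Who will develop foot pain is not known at consent, so the sponsor should also say how events before group entry are captured, and what applies to children without foot pain and to Phases II and III.
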